 - Phospho-S6 (phosphorylated ribosomal protein S6)
 - Phospho-Akt
 - Cyclin D1
- Evaluation of the tumor specimens and description of staining intensity will be performed by [name].
- The baseline staining pattern for the various markers will be correlated with progression-free survival at 6 months (PFS6).
- Immunostains will be repeated on tumor specimens obtained from patients who undergo surgery on protocol therapy. Changes in tissue biomarkers from baseline to surgery will be summarized descriptively.

Blood biomarkers

Blood samples for future research

- Two tubes of blood for plasma and serum to be used in future research studies at MSKCC will be collected from all patients
 - Kits for these samples will be provided to each participating site by MSKCC and collected plasma and serum samples will be bulk shipped to MSKCC every six months.
 - Instructions for processing these samples, as well as shipment information, are in the Lab Manual.

Putative FLL-HCC tumor biomarkers to be measured within 2 weeks of initiating study therapy and every 12 weeks during the protocol in all patients.

- **AFP**
 - AFP will be collected and resulted at respective site's laboratory.
- **Plasma neurotensin**
 - **Patients should be fasting 10 - 12 hours prior to collection of specimen. Patients should not be on any antacid medication or medications that affect gastroentero-intestinal function, if possible, for at least 48 hours prior to collection.**
 - A 10mL sample will be drawn into an EDTA z top tube provided by the Interscience Institute through LabCorp. The serum should be separated from the whole blood as soon as possible to maintain the integrity of the sample. Once the serum has been

MEMORIAL SLOAN-KETTERING CANCER CENTER IRB PROTOCOL

IRB#: 11-211 A(6)

separated it should be frozen immediately until the sample is ready to be shipped. All neurotensin samples will be processed at Inter Science Institute [name]. Further details regarding sample preparation, packaging, and shipping are found in the study lab manual.

- **Serum unsaturated vitamin B12 binding capacity (transcobalamin)**
 - **Must draw before Schilling test, transfusions, or B₁₂ therapy is started.**

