14.0 BIOSTATISTICS

Primary efficacy endpoints for Part 1 of protocol

- The primary efficacy endpoints for Part 1 of the study is progression-free survival at 6 months (PFS6).
- A progression event refers to the first evidence of radiographic disease progression, clinical progression as determined by study investigators, or death.
- Imaging performed in 6 months will be used to determine PFS6.
- PFS6 will be defined as the percentage of patients who are alive and have not experienced a progression event as defined above at 6 months from the date that study therapy was initiated. Patients that come off study before the 6 months scan will be considered events for the primary endpoint analysis.
- PFS6 will be assessed using a Simon's minimax two stage design, hypothesizing an improvement in PFS6 from 40% to 64% with the study regimen. Sixteen patients will be enrolled onto each of Arms A, B and C for a total of 48 patients in the first stage. Accrual will stop till the progression status at 6 months is obtained on all 16 patients in each arm. If 6 or less patients in one arm are progression free at 6 months the regimen in that arm will be terminated; otherwise, if 7 or more patients are alive and progression free at 6 months, enrollment will be extended in that arm to 28 patients (maximum total of 84 patients). At the end of stage 2, the respective regimens will be declared promising if 15 or more of the 28 patients in each arm are alive and progression free at 6 months. The design assumes a type I error (falsely accepting a non-promising therapy) and type II error (falsely rejecting a promising therapy) both set to 10%.

Figure 4: Simon's minimax 2 stage design (schematic applicable for each study arm)

- The probability of early termination due to drug inefficacy is 53%. In the event that 2 or more arms show promising activity, we will use the “pick the winner” format based on the randomized phase II clinical trials approach proposed by Simon et al. In this case, the regimen that has at least 15 patients progression free at 6 months and exceeds by at least 2 patients the number of progression free patients in the second best arm would be declared the winner. The probability of selecting the better regimen is 85%; the probability that no regimen is selected is 7%, while the probability of a tie is approximately 6% [149].

Secondary endpoints

- Secondary endpoints are:
 - Median PFS
 - Median overall survival (OS)

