 - Objective response rate by RECIST 1.1 guidelines
 - Rate of conversion to resectable status
 - Safety and toxicity
 - Correlative serum and tissue biomarker studies.
- Kaplan-Meier PFS will be measured from the date that study therapy is initiated until the date of

first evidence of radiographic disease progression, global clinical deterioration as determined by study investigators, or death.

- Kaplan-Meier OS will be measured from the date that study therapy was commenced until the date of death.
- Objective responses will be reported using RECIST guidelines (version 1.1). Objective response will be estimated using binomial proportions and exact 95% CIs will be provided.
- Conversion to resectable status to be determined by hepatobiliary surgeons in conjunction with radiological assessment of response to therapy.
- Adverse events/toxicity will be monitored and recorded using the CTCAE version 4.0 and summarized descriptively.
- Baseline serum measurements will be correlated with PFS6 (binary endpoint) using Fisher's exact test for categorical serum measurements and using Wilcoxon rank sum test for continuous measurements. For each time point at which serum measurements are collected, changes in the different binary serum markers from baseline will be correlated with PFS6 using conditional logistic regression to account for the paired nature of the data while Wilcoxon signed-rank test will be used for continuous measurements.
- Associations between baseline tissue biomarkers and PFS6 will be assessed using Fisher's exact test for categorical biomarkers, trend tests for ordinal biomarkers and Wilcoxon rank-sum test for continuous biomarkers. For patients undergoing surgery, changes in tissue biomarkers from baseline to surgery will be summarized descriptively in an exploratory fashion.

Exploratory analysis for Part 2 of protocol (combination therapy).

- PFS will be evaluated for patients who were on Arm A (everolimus) or Arm B (EDT) during Part 1 of the study who subsequently received combined everolimus + EDT during Part 2.
- PFS will be measured as the time from the start of the combination therapy till progression or death whichever comes first.

Biomarker analysis and data interpretation

- Baseline tissue biomarkers will be correlated with PFS6.
- Baseline levels of hormones will be correlated with PFS6.
- Baseline levels of tumor markers will be correlated with PFS6.

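### The tests planned for marker change against PFS6 do not test that association: the signed-rank test never uses PFS6, and conditional logistic regression with PFS6 as outcome cannot be fitted

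*Combined protocol and SAP*

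**What the plan says.** All the relevant text is in the combined protocol and SAP.

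- **Outcome.** In Section 14.0, "PFS6 will be defined as the percentage of patients who are alive and have not experienced a progression event" at 6 months from the start of study therapy. The Secondary endpoints text treats it as binary, so each patient has one PFS6 value.
- **Baseline markers.** "Baseline serum measurements will be correlated with PFS6 (binary endpoint) using Fisher's exact test for categorical serum measurements". Continuous baseline values get a rank-sum test. Both methods compare patients with and without PFS6.
- **Change from baseline, aim.** At each serum time point, "changes in the different binary serum markers from baseline will be correlated with PFS6".
- **Change from baseline, methods.** The same sentence then names the tests for binary and continuous markers: "using conditional logistic regression to account for the paired nature of the data while Wilcoxon signed-rank test will be used for continuous measurements". The pairing can only be baseline with follow-up in the same patient. No outcome variable, stratum or interaction term is named.
- **Timing.** Section 10.0 (Blood biomarkers): "Putative FLL-HCC tumor biomarkers to be measured within 2 weeks of initiating study therapy and every 12 weeks during the protocol in all patients".
- **Other text on change.** Section 14.0 (Biomarker analysis and data interpretation) plans to relate maximum change in tumor biomarkers, and achievement of chemical castration, to PFS6. It names no test for either.

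**The concern.** The stated aim is a comparison between patients: does a marker's change differ between those who reach 6 months progression-free and those who do not? The methods named are within-patient methods. The pairing is already used once each patient's change has been computed; what remains is a two-group comparison, which is how the plan handles baseline markers in the sentence before.

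Followed literally, the plan produces two problems:

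- For continuous markers, a significant result means only that the marker moved on treatment. Estrogen deprivation therapy is intended to suppress serum estrogens, testosterone and FSH, so movement in the hormones is expected whether or not suppression has any bearing on outcome. A marker whose change truly separates the PFS6 groups can be missed if the movements offset each other.
- For binary markers, the model on its natural reading returns no estimate, so a replacement would have to be chosen after the data are seen.

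Correlative serum and tissue biomarker studies are a listed secondary endpoint, and Section 10.0 describes them as particularly important in a disease this rare.

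**Working it through.** The plan states no alpha, power, sample size or effect size for these analyses, so there is no figure of its own to reproduce. The check is on the structure of the tests, followed by an illustration.

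**1. Signed-rank test**

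Let d_i be the change from baseline in patient i. The statistic is W = the sum of rank(|d_i|) over patients with d_i > 0. PFS6 does not appear in W, so permuting the PFS6 labels leaves W and its p-value unchanged. Running the test separately within each PFS6 group still does not compare the groups.

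**2. Conditional logistic regression, PFS6 as outcome, patient as stratum**

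For a patient with marker values x1 (baseline) and x2 (follow-up), the conditional likelihood is exp(β·Σ y_j x_j) divided by the sum of the same expression over all arrangements of the outcomes with the same total.

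- PFS6 = yes, outcomes (1,1): exp(β(x1+x2)) / exp(β(x1+x2)) = 1.
- PFS6 = no, outcomes (0,0): 1 / 1 = 1.

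Every patient contributes a likelihood of 1 for any β. The log-likelihood is flat at 0 and β is not estimable. A fit to 84 simulated patients with two time points dropped all 84 strata and the Hessian could not be inverted.

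**3. Conditional logistic regression, marker as outcome**

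Three forms were fitted to the same simulated data, in which follow-up marker status depended on PFS6:

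| Terms | Result |
|---|---|
| time + PFS6 main effect | not estimable: PFS6 is constant within patient |
| time only | p = 0.25; tests only whether the marker changed |
| time + time × PFS6 | interaction −2.37, p = 0.003 |

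Only the last form tests the stated association, and the plan does not specify it.

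**4. Size of the error for continuous markers (illustration)**

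Assumed: 56 patients (2 × 28, two arms at full size), 28 in each PFS6 group, SD of change 1, two-sided 5%.

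| Scenario | Signed-rank rejects | Rank-sum on change rejects |
|---|---|---|
| All fall 0.5 SD, no link to PFS6 | about 95% | about 5% |
| Groups move 0.5 SD in opposite directions | about 3% | about 95% |

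Both 95% figures agree with a normal approximation, using 3/π ≈ 0.955 as the efficiency of the rank tests relative to the t-test:

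- Signed-rank, first row: 0.5 × √56 = 3.74; 3.74 × √0.955 = 3.66; Φ(3.66 − 1.96) = Φ(1.70) ≈ 0.955.
- Rank-sum, second row: 1.0 / √(2/28) = 3.74, and the same steps give about 0.955.

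Signed-rank falls below 5% in the second row because the equal split is fixed. If group sizes vary at random, it is about 5%.

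**5. Sensitivity to the assumptions**

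With about 54% progression-free:

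| Scenario | n | Signed-rank | Rank-sum |
|---|---|---|---|
| Same change of −0.8 SD in both groups | 28 | 98% | 4% |
| Same change of −0.8 SD in both groups | 84 | 100% | 5% |
| Opposite changes, 1.6 SD apart, cancelling overall | 28 | 1% | 97% |
| Opposite changes, 1.6 SD apart, cancelling overall | 84 | 1% | 100% |

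Less extreme cases soften the figures:

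- At n = 28 with a uniform fall of 0.5 SD, signed-rank rejects in about 69%.
- With 56 patients split 36/20 and opposite 0.5 SD changes, it rejects in roughly 12 to 14%.
- With 28 per group, if one group falls 1 SD and the other is flat, it rejects in about 91% against 94% for rank-sum, but because the pooled marker moved and not because of PFS6.

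**The case against.** Several points can fairly be made for the plan.

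- **Reach.** Correlative studies are the last of six secondary endpoints. The primary PFS6 rule, the stage 1 stopping rule, the selection between arms, safety and data collection are all unaffected, and the wording can still be corrected before analysis. This stands, and it limits the consequence. It does not make the tests valid.
- **The conditional model depends on a reading.** The plan names no outcome or terms, and a version with the marker as outcome and a time-by-PFS6 term would work. This stands as far as it goes: the method is not unusable in principle. But the natural reading cannot be fitted, and the workable version is not in the text. Its failure would at least be visible, as no estimate is produced.
- **Few binary serum markers.** The repeated assays in Section 10.0 are quantitative, so the binary half may have little to act on. That makes the signed-rank error the more important of the two.
- **The figures are illustrative.** The effect sizes are assumed, and the missed-association case relies on movements that cancel. This is correct; the percentages are scenario results and not the trial's expected error rates. That the signed-rank test ignores PFS6 depends on none of them.
- **A false claim also needs a misreading.** A signed-rank result contains no PFS6 comparison. True, but the plan names that result as its answer to the PFS6 question.
- **Rank-sum on change is not a complete remedy.** Draws are every 12 weeks, and patients who come off study before the 6-month scan count as events. By the second follow-up draw (week 24), few patients without PFS6 may still be measured on Part 1 therapy. This stands and is taken up in the fix.

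**Conclusion.** The concern holds. For continuous serum markers the named test cannot measure association with PFS6, whatever the data. For binary markers the named model is not estimable with PFS6 as outcome and the patient as stratum, and the one form that would work is not specified. No other section supplies a valid test of change against PFS6.

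Under the assumed 56 patients, equal groups and 0.5 SD changes, the signed-rank test is significant in about 95% of trials when there is no association, and in about 3% when there is a strong one in opposite directions. The exact percentages depend on those assumptions; the structural failure does not. The error is confined to a secondary correlative endpoint, but the text is wrong as written and should be corrected before any marker analysis is run.

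**What to change.** Replace the sentence on change from baseline in Section 14.0 (Secondary endpoints):

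- **Continuous markers.** At each time point, compute each patient's change from baseline and compare patients with and without PFS6 by the Wilcoxon rank-sum test. Logistic regression of PFS6 on change, adjusted for baseline value and arm, is an alternative.
- **Binary markers.** Cross-tabulate category of change (stayed negative, converted, reverted, stayed positive) against PFS6, with Fisher's exact test or exact logistic regression. If conditional logistic regression is preferred, state that the marker is the outcome, the patient is the stratum and the time-by-PFS6 interaction is the quantity tested.
- **Signed-rank test.** Keep it only to describe on-treatment change.

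Two further sentences would complete the correction:

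- Name the tests for the maximum-change and chemical-castration bullets under Biomarker analysis and data interpretation.
- State how patients with no draw at a time point are handled, for instance by making the week 12 draw the main time point, limiting that analysis to patients still progression-free and measured then, and reporting the number in each PFS6 group.

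The cost is a few sentences of SAP wording. No extra patients, samples or time are needed.

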3.1 BACKGROUND AND RATIONALE

3.2 Fibrolamellar hepatocellular carcinoma (FLL-HCC): Background

FLL-HCC is an extremely rare malignancy. According to SEER data, only 68 cases of FLL-HCC were diagnosed between 1986 and 1999, comprising only 0.85% of all primary liver cancers [1]. International series have reported an FLL-HCC frequency ranging from 0.6% in Thailand [2] up to 5.8% in Mexico [3]. The incidence of FLL-HCC may be even higher given that a number of cases may be misdiagnosed as typical hepatocellular carcinoma (HCC) [1,4]. FLL-HCC is usually diagnosed in the 3rd to 4th decade of life and occurs equally in both sexes unlike typical HCC which has a male predominance [1,5-7]. In addition, FLL-HCC appears to occur mainly in Caucasian patients and is extremely rare in those of Asian descent [8,9]. Signs and symptoms are non-specific and include hepatomegaly and/or an abdominal mass with pain, weight loss, digestive symptoms and malaise [10-12]. FLL-HCC typically arises from normal liver parenchyma and is associated with normal α -fetoprotein (AFP) levels [13]. Serum markers that have been found to be elevated in patients with FLL-HCC include neurotensin, vitamin B12 binding capacity and plasma des- γ carboxy-prothrombin, and may represent potential tumor markers for this disease [5,14-17]. Radiographically, FLL-HCC appears as a well-defined lobulated, heterogeneous mass with central scarring, and is differentiated from typical HCC by the presence of normal surrounding liver tissue,

its tendency for unifocal disease, and the absence of vascular invasion [18]. On pathological examination, FLL-HCC is characterized by layers of fibrous stroma, and demonstrates an expanding growth pattern in contrast to the invasive pattern of typical HCC [12,16,19]. Locoregional lymph node metastases are present in up to 70% of patients at presentation and are associated with a high risk of relapse and poorer prognosis [5,11,20]. Distant metastases are less common.

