3.5.3 Men

In men, approximately 20% of endogenous estrogens are produced by the testes while the remaining 80% are the result of peripheral aromatization of testicular and adrenal androgens [55]. Although aromatase inhibitors can reduce estradiol to near undetectable levels comparable to those seen in postmenopausal women, the response is not complete in all patients [55]. Reasons for this observation are several-fold. First, as a function of having higher baseline androgen levels, men have higher estrogen levels compared to postmenopausal women [56]. In addition, aromatase inhibitors are ineffective against testicular estrogen production [57]. Furthermore, increased gonadotropins as a result of exposure to an aromatase inhibitor [58] may provoke an increase in androgen substrate which competes for aromatase, leading to secondary resistance [55]. These considerations provide the basis for adding a GnRH agonist to an aromatase inhibitor for the management of men with breast cancer. Experience with this combined regimen is mainly anecdotal thus far, and results have been mixed with respect to efficacy, possibly due to the uncertain effects of GnRH agonists on testicular estrogen production [59,60]. A phase II study of goserelin and anastrozole in men with advanced hormone receptor positive breast cancer has been completed and results are pending (NCT00217659, www.clinicaltrials.gov).

The side effects of prolonged androgen deprivation due to GnRH agonists are analogous to those associated with chemically induced menopause in premenopausal women. The most extensive experience with GnRH agonists in men comes from the prostate cancer literature. Common side effects include decreased libido, gynecomastia and hot flushes [61]. There is also a significantly higher risk of developing skeletal fractures, osteoporosis, and features of metabolic syndrome including diabetes and cardiovascular events [62,63]. Healthy lifestyle modifications and close

monitoring of glucose and lipid homeostasis as well as bone health (see section 3.5.6) are recommended as an integral part of the management plan [63].

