8.3 Within 2 weeks of study treatment including first day of treatment

- Complete medical history and physical examination, including ECOG performance status (Lansky performance status for patients 12-16 years old), height/weight/body surface area.
- Complete blood count (CBC) and differential, comprehensive metabolic panel (Na, K, Cl, HCO₃, BUN, creatinine, AST, ALT, alkaline phosphatase, glucose), calcium, phosphorus, LDH, and ammonia
- Liver function tests (total bilirubin, albumin, INR/PTT)
- Fasting glucose and lipid profile including triglycerides and total cholesterol.
- Urinalysis.
- Electrocardiogram
- AFP
- Baseline plasma neurotensin, unsaturated vitamin B12 binding capacity, and des- γ -carboxyprothrombin
- Baseline serum estrone, estradiol, testosterone and follicle stimulating hormone (FSH) in all patients.
- Quantitative PCR for hepatitis C and hepatitis B as applicable. If hepatitis B surface antigen and/or hepatitis B core antibody are positive, results must be reported **before** Cycle 1 Day 1 of study treatment. Hepatitis C and hepatitis B quantitative PCR, as applicable, will be repeated every 3 months.
- Patients known to be infected with hepatitis C will be monitored as clinically indicated.
- Patients will be asked to give a blood sample and have their biopsy specimen available for future research studies.

- Negative pregnancy test (serum hCG) result in women of child bearing potential within 7 days before Cycle 1 Day 1 of study treatment. Negative pregnancy test (serum hCG) on Cycle 1 Day 1 is adequate.

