9.2 Part 1, Arm B: EDT (letrozole and leuprolide)

MEMORIAL SLOAN-KETTERING CANCER CENTER IRB PROTOCOL

IRB#: 11-211 A(6)

Day 1 of Cycle 1: Baseline serum estrone, estradiol, testosterone and follicle-stimulating hormone (FSH) level in all patients (if not already done). If estradiol is within postmenopausal range for women (≤ 30 pg/mL) and testosterone is within the castration range for men (≤ 50 ng/dL), patient does not have to have hormones retested at week 2 and may begin letrozole 2.5 mg po QD Week 2 of Cycle 1.

- Day 1 of Cycle 1: Leuprolide 7.5 mg IM will be administered by a nurse in clinic.
- Week 2 of Cycle 1 (+/- 7 days): Women with estradiol not within postmenopausal range (≤ 30 pg/mL) or men with testosterone not within the castration range (≤ 50 ng/dL), measure serum estradiol and testosterone; if estradiol is within postmenopausal range (≤ 30 pg/mL) and testosterone is within the castration range (≤ 50 ng/dL), begin letrozole 2.5 mg po QD. Otherwise, retest hormones on C2W1. Consult MSKCC PI if hormones are still not within range. to further discuss the letrozole start date.
- Letrozole will be dispensed by the respective institutions' pharmacies and will be taken at home. Patients will be instructed to take letrozole at the same time each day, consistently with food or without food, and swallowed whole with a glass of water.
 - If a dose is missed, they will be instructed to take it as soon as they remember up until 12 hours past the schedule dose time. If it is almost time to take the next dose, they will be instructed to skip the missed dose and just take the scheduled dose. They will be instructed NOT to take 2 doses at the same time [137].
 - If vomiting occurs after taking letrozole, the subject should not take a replacement dose on that day. The subject should resume taking letrozole at the next scheduled dose on the following day. If vomiting persists, the subject should be instructed to notify the investigator. If a subject vomits what appears to be an intact tablet(s), the subject should not take a replacement dose on that day because it is not possible to determine how much drug has actually been absorbed.
 - Patients will be provided with a pill diary to record the date and time of day that letrozole was taken.
- Continue leuprolide 7.5 mg IM every 4 weeks (+/- 7 days).
- One cycle of EDT corresponds to 4 weeks of treatment.
- Letrozole and leuprolide should be administered concurrently at all times.

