 - A 0.5 mL sample will be drawn into a red-top, gel-barrier, or EDTA tube provided by LabCorp. The serum should be separated and put into a plastic transfer tube and frozen immediately until it is ready to be shipped. All unsaturated vitamin B12 binding capacity samples will be processed at LabCorp [name]. Further details regarding sample preparation, packaging, and shipping are found in the study lab manual.
- **Serum des-γ-carboxyprothrombin (DCP)**
 - No special patient preparations are necessary.
 - A 2 mL sample will be drawn into a red-top or gel-barrier tube provided by LabCorp. The serum should be separated, put into a plastic transfer tube, and frozen immediately until it is ready to be shipped. All unsaturated serum DCP samples will be processed at LabCorp [name]. Further details regarding sample preparation, packaging, and shipping are found in the study lab manual.

Serum hormones

- All serum hormones will be processed and resulted at the respective site they were drawn at. Patients on the EDT-containing study arms (Arms B and C) will have blood drawn for the following serum hormones:
 - Serum estrone
 - Serum estradiol
 - Serum follicle stimulating hormone (FSH)
 - Serum testosterone
- Serum hormones will be measured within 2 weeks of initiating study therapy. Serum estradiol and testosterone will be measured again during Week 2 of therapy if required per protocol. All hormones (estrone, estradiol, FSH, testosterone) will be measured every 12 weeks thereafter.

• Sample storage and destruction

Blood and tumor samples collected for biomarker analysis and any other components from the cells may be stored for up to 20 years for future scientific investigations related to FLL-HCC. Study subjects maintain the right to have the sample material destroyed at any time by contacting the principal investigator. MSKCC will be the exclusive owner of any data, discoveries or derivative materials from the sample materials and is responsible for the destruction of the sample(s) at the request of the research subject through the principal investigator, at the end of the storage period, or as appropriate (e.g. the scientific rationale for experimentation with a certain sample type no longer

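### Baseline hormone levels are to be tested against PFS6 with a rank-sum test that makes no provision for sex, so a sex difference can be read as a hormone effect and power for a within-sex association can be lost

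*Combined protocol and SAP*

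**What the plan says.** Section 14.0 (Biostatistics), under secondary endpoints, says "Baseline serum measurements will be correlated with PFS6 (binary endpoint") by Fisher's exact test when the measurement is categorical and "using Wilcoxon rank sum test for continuous measurements". Under biomarker analysis it adds "Baseline levels of hormones will be correlated with PFS6". Estradiol, estrone, testosterone and FSH are continuous laboratory values, so the rank-sum test applies to them. Section 14.0 names no stratified or adjusted test and mentions neither sex, menopausal status nor age. The only stratification factor for randomization is study site (Section 15.2).

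Elsewhere the protocol handles these hormones by sex:

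- Section 4.3 checks estradiol in females and testosterone in males after the first leuprolide injection.
- Section 9.2 applies an estradiol cutoff to one sex ("Women with estradiol not within postmenopausal range") and a testosterone cutoff to the other.
- Section 3.5.3 says men have higher androgen levels, and that "men have higher estrogen levels compared to postmenopausal women".
- Section 3.2 says the disease "occurs equally in both sexes unlike typical HCC which has a male predominance", so a roughly even mix is to be expected.

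The documents disagree on who is sampled. Section 8.3 asks for "Baseline serum estrone, estradiol, testosterone and follicle stimulating hormone (FSH) in all patients". The serum hormones part of Section 10.0 says "Patients on the EDT-containing study arms (Arms B and C) will have blood drawn for the following serum hormones".

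**The concern.** A rank-sum test without strata puts all patients into one ranking. If a hormone runs higher in one sex, part of each patient's rank records sex rather than that patient's hormone level relative to others of the same sex. Two things can follow:

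- If PFS6 differs by sex for any reason, the test can reject with no hormone association within either sex.
- If there is a within-sex association, the between-sex spread in ranks acts as noise and power falls.

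Estrogen biology is the trial's rationale (Sections 1.0 and 3.5), and Section 10.0 stresses the value of correlative studies in a disease this rare. A hormone result would therefore be read as evidence about mechanism, and a sex difference is not that.

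**Working it through.** **The plan's own figures.** Section 14.0 gives no alpha, power or sample size for the hormone analyses, so there is no figure of that kind to reproduce. The primary design does reproduce. An exact two-stage binomial (16 then 28 patients per arm, stop at 6 or fewer, success at 15 or more, 40% v 64%) gives type I error 0.0989, power 0.902 and early termination 0.527, against the stated 10%, 90% and 53%. The present point does not touch it.

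**Inputs from the documents.** N = 84 is the maximum, 28 in each of three arms (Section 14.0). An even sex mix follows Section 3.2.

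**Assumptions.** The documents give no hormone distributions and no PFS6 by sex. I take normal values within sex, a shift of d within-sex SDs between the sexes (0.5 to 6), PFS6 of 60% v 40% by sex for the false-positive case, and a two-sided 5% test.

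**Step 1: how much of the ranking is sex.** Let θ = Φ(d/√2), the chance that a random patient of the higher-level sex exceeds a random patient of the other. With equal numbers, the share of rank variance due to sex is 3(θ − 0.5)². At d = 1, 3 × 0.260² = 0.20.

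**Step 2: pooled rejection with no within-sex association.** The higher-level sex supplies 60% of the patients with PFS6 and 40% of those without. The chance A that a patient with PFS6 outranks one without is

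A = 0.6×0.6×θ + 0.4×0.4×(1 − θ) + ½(0.6×0.4 + 0.4×0.6) = 0.40 + 0.20θ.

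With 42 patients in each PFS6 group, SE = √[(84 + 1)/(12 × 42 × 42)] = 0.0634. Then z = (A − 0.5)/SE, and the rejection rate is Φ(z − 1.96) + Φ(−z − 1.96). Simulation of the pooled and the sex-stratified (van Elteren) tests agrees:

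| d (SD) | θ | Rank variance due to sex | A | z | Pooled, formula | Pooled, simulated | Stratified, simulated |
|---|---|---|---|---|---|---|---|
| 0.5 | 0.638 | 6% | 0.528 | 0.44 | 7% | 7% | 5% |
| 1 | 0.760 | 20% | 0.552 | 0.82 | 13% | 13% | 4% |
| 2 | 0.921 | 53% | 0.584 | 1.33 | 26.5% | 27% | 6% |
| 6 | 1.000 | 75% | 0.600 | 1.58 | 35% | 36% | 5% |

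If PFS6 is the same in both sexes, A = 0.5 at every d and the pooled test keeps its 5% level.

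**Step 3: power for a within-sex association** (log odds ratio 0.8 per within-sex SD, no sex effect, simulated, N = 84):

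| d (SD) | Pooled | Stratified |
|---|---|---|
| 0.5 | 0.89 | 0.91 |
| 1 | 0.82 | 0.89 |
| 2 | 0.59 | 0.90 |
| 6 | 0.36 | 0.90 |

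With no separation, stratifying costs almost nothing: 0.90 pooled v 0.89 stratified for a within-sex AUC of 0.70. If a sex effect on PFS6 (64% v 40%) runs against the hormone effect, pooled power is 0.43 at 1 SD and 0.09 at 2 SD, against about 0.88 stratified.

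**Step 4: the smaller sample.** If only Arms B and C are sampled, N is at most 2 × 28 = 56. Pooled power is then 0.65 at 1 SD and 0.41 at 2 SD, against about 0.74 stratified. With SE = √[57/(12 × 28 × 28)] = 0.0778, the Step 2 formula gives pooled rejection rates of 10%, 19% and 25% at 1, 2 and 6 SD.

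**The case against.** Several points on the other side stand.

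**Pooling is not stated.** A reader might infer that the plan chooses to analyze men and women together. It does not say so. Pooling is what the named test does when nothing else is specified.

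**A reader might infer that the test mainly measures sex for all four hormones.** The documents do not support that. The comparison in Section 3.5.3 is with postmenopausal women, while Section 1.0 describes a disease of adolescents and young adults. Section 3.5 reports young men with this tumor and raised estrogen, which argues against clean separation of estradiol or estrone. No sex difference is given for FSH. At 1 SD, sex carries only 20% of the rank variance. Wide separation is plausible mainly for testosterone.

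**A reader might infer that any within-sex association would be hidden.** With no sex effect on PFS6, power is reduced, to 0.36 at worst in the table, but not removed. It falls to near 5% only if a sex effect opposes the hormone effect and separation is wide.

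**The false-positive problem needs PFS6 to differ by sex.** No passage says that it does.

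**If absolute exposure matters, pooling has more power.** If the hormone level across both sexes drives PFS6 (log odds ratio 0.5 per SD), power is about 0.67 pooled v 0.56 stratified at 1 SD, and 0.86 v 0.53 at 2 SD. This is a real cost of stratifying. However, the extra power comes from the contrast between men and women, which cannot be told apart from a sex effect on prognosis.

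**Sex is not the only source of variation.** Menopausal status and puberty (enrollment starts at age 12) also matter, and stratifying by sex does not remove them.

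**Conclusion.** The point holds in a limited form. The plan assigns baseline hormones a rank-sum test with no provision for sex, in a population where the protocol itself reads hormones by sex. The harm depends on how far each hormone separates the sexes. Under the stated assumptions it is slight at 0.5 SD (7% v about 5% false positives; power 0.89 v 0.91) and large at 2 SD or more (27% to 36%; power 0.59 to 0.36 against 0.90). The false-positive figures also require the assumed 60% v 40% difference in PFS6 by sex.

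The case for stratifying does not depend on knowing the separation. It costs almost nothing if there is none, and it keeps a sex difference from being read as a hormone effect if there is one. The figures use N = 84, which requires all three arms to pass stage 1. Under the Section 10.0 sampling rule the maximum is 56. This is a cheap improvement to a secondary correlative analysis that carries no decision rule.

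**What to change.** In Section 14.0, specify the sex-stratified (van Elteren) Wilcoxon test for baseline estradiol, estrone, testosterone and FSH against PFS6, and report medians by sex and PFS6 status. In each sex, take the rank sum of patients with PFS6 minus its null expectation, weight it by 1/(n + 1) with n the number of patients of that sex, and add across the sexes. The pooled test can stay as a descriptive companion for readers interested in absolute exposure, labeled as not separable from sex.

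Reconcile Section 8.3 (hormones in all patients, up to 84) with the serum hormones part of Section 10.0 (Arms B and C, up to 56), and state the analysis N.

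The cost is a line or two of text for the test and one correction for the sampling rule. The stratified test needs no new patients or assessments. The statistical price is the power given up if absolute level across the sexes is what matters.
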